8.3 ADVERSE EVENTS

The adverse event verbatim descriptions (investigator terms from the CRF) will be classified into medical terminology using the Medical Dictionary for Regulatory Activities (MedDRA). Adverse events will be coded to primary System Organ Class (SOC) and preferred term (PT) using MedDRA, Version 19.0.

A treatment-emergent adverse event (TEAE) is defined as an AE that initiated or worsened on or after the date of first dose of study drug up to the end of safety follow-up. For AEs occurring on

the first dosing day, if the start time cannot be ascertained, the event will be counted as treatment-emergent.

Only those AEs and SAEs that are treatment-emergent will be included in summary tables. All AEs and SAEs, treatment emergent or otherwise, will be presented in subject data listings.

TEAEs and SAEs will be summarized by treatment group. The incidence of AEs will be reported as the number (percent) of subjects with AEs within SOC and PT. The incidence of AEs with onset within Weeks 1-12 and Weeks 13-24 will also be summarized. Subjects will be counted only once within a SOC and PT, even if the subject experienced more than one event within a specific SOC and PT. The number (percent) of subjects with events will also be summarized by highest CTC grade as well as by closest relationship. If more than one event occurred with the same preferred term for the same patient, the patient will be counted only once for that preferred term using the most severe or related occurrence for the summary by severity, or relationship to Study Drug, respectively.

Patient counts and percentages will be presented for the following summaries by treatment group and overall:

- Overall summary of TEAE's
- All TEAEs by SOC and PT;
- TEAEs related to study drug by SOC and PT;
- TEAEs by relationship to study drug by SOC and PT;
- TEAEs by highest severity grade by SOC and PT;
- Summary of TEAE meeting Dose-Limiting Toxicity Criteria (Study Days 1 – 21) by SOC and PT;
- All TESAEs by SOC and PT;
- All AEs leading to discontinuation of study drug by SOC and PT;

A subject data listing of all AEs leading to death, if any, will be provided.

Following Database Lock 1 and 2 (as described in [Section 11](#)), two versions of the Overall summary of TEAE's and all TEAE's by SOC and PT, AEs leading to discontinuation of study drug by SOC and PT, and all TESAEs by SOC and PT will be created. Version 1 will include only frozen AE data. Version 2 will include all AEs.

8.5 INFUSION-RELATED REACTIONS, HYPERSENSITIVITY REACTIONS, AND ANAPHYLAXIS

The infusion related reactions, hypersensitivity reactions, and anaphylaxis events will be summarized by treatment group using frequencies (number and percent of subjects).

8.6 INFECTION DETAILS

A subject listing for the infection details captured in CRF will be provided. Additionally, a summary table will be generated summarizing types of infection and type of infectious agent if known (e.g., bacteria, virus, fungus, etc.).

8.7 DIALYSIS DETAILS

For each dialysis, the duration in minutes, target dry weight and frequencies (number and percentage) of dialysis access used, and net ultrafiltration volume will be summarized descriptively.

8.8 VITAL SIGNS, PHYSICAL EXAMINATION FINDINGS, AND ECG

8.8.1 Vital Signs

According to the collection schedule, the observed value of vital signs parameters (diastolic and systolic blood pressure, pulse rate, respiration rate and temperature) and change from baseline in these parameters will be summarized in three separate tables. One for pre-dialysis by visit, with baseline being the pre-dialysis values at week -1. One for post-dialysis by visit, with baseline being the post-dialysis values at week -1. And the third table for pre- and post-infusion by visit, with baseline being the pre-infusion values at that visit; in this table change from pre- to post-infusion within each infusion session will also be provided. As pre-dialysis weight is collected in a different schedule than other vital signs, two separate tables for pre-dialysis weight and BMI, post-dialysis weight and BMI will be provided separately.

In addition, the percentage of patients exceeding pre-defined absolute and relative threshold values across the entire treatment period, across the entire safety follow up period, and across both of these period will be summarized (see

Table 3). When calculating the percentages, numerator will be the number of subjects with normal baseline with respect to the specific criterion and at least 1 post-baseline outlier value within the analysis period; and denominator will be the number of subjects with a baseline and at least 1 post-baseline assessment within the analysis period. A subject may be counted more than in multiple categories for a given parameter. Three tables will be provided separately for pre-dialysis values, post-dialysis values and pre-/post-infusion values. All results (regardless of scheduled or unscheduled) will be considered in this summary.

Table 3: Pre-defined Threshold Value for Vital Signs

Parameter	Criteria
Systolic Blood Pressure (SBP)	>20 mmHg increased or decreased from baseline
SBP	> 30 mmHg increased or decreased from baseline
SBP	>180 mmHg
SBP	<95 mmHg
Heart Rate (HR)	>100 beats per minute
HR	<50 beats per minute
Respiration Rate	>24 breaths per minute
Weight (pre-dialysis)	>5 kg increased from baseline pre-dialysis weight
Weight (pre-dialysis)	>5 kg decreased from baseline pre-dialysis weight
BMI	>10% increased from baseline
BMI	>10% decreased from baseline

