3.2 Study Schematic

Figure 2 Dose Escalation Schematic

- ¹ If the MTD is not exceeded, dose escalation may continue.
- ² If the MTD is exceeded, a lower dose, including previously studied dose, may be selected.

The MTD assessment will be based on safety data from Weeks 1 to 3. If more than 2 of 8 active patients in a cohort experience a DLT, the MTD will be considered to have been exceeded.

The planned doses shown here may be adjusted based on accruing PK, PD, and safety data. The highest dose that will be studied is a cumulative dose of 360 mg. Expansion cohorts to further evaluate doses below the dose that exceeded the MTD may be initiated at any time.

The randomization ratio within each cohort will be 8:2 (COR-001 to placebo).

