2. STATISTICAL METHODS

2.1 GENERAL CONSIDERATIONS

Unless otherwise specified, all study-collected data will be summarized by treatment group using descriptive statistics, graphs, and/or raw data listings. Descriptive statistics for continuous variables will include number of patients (n), mean, standard deviation (SD), median, quartiles (Q1 and Q3), minimum (min) and maximum (max) values. Analysis of categorical variables will include frequency and percentage.

P-values will be rounded to three decimal places. If a p-value is less than 0.001 it will be reported as “<0.001.” If a p-value is greater than 0.999 it will be reported as “>0.999.” 95% confidence intervals will be estimated for pharmacodynamic endpoints.

For the analyses to be used for SRC, the subjects will be summarized by treatment group within each cohort. The placebo group will not be pooled.

For the final CSR report, the subjects will be summarized according to their treatment group. The placebo subjects at each cohort will be pooled into one group, and the subjects treated with COR-001 will be summarized based on the dosing regimen.

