8.8.2 Physical Examination

A subject listing of physical exam findings of signs of infection will be provided.

In addition, Physical examination clinically significant new or worsening findings will be reported as adverse events and will therefore be summarized as described for adverse events.

8.8.3 12-Lead ECG

ECG interpretation (normal vs. abnormal) will be summarized using frequency and percentage at each visit by treatment group. Observed values and change from baseline in ECG intervals (PR, QT, HR, and QTcF), rhythm and heart rate will be summarized descriptively at each visit by treatment group.

The percentage of patients exceeding pre-defined absolute and relative threshold values across the entire treatment period, across the entire safety follow up period, and across both of these periods will be summarized (see [Table 4](#)). When calculating the percentages for the criterion related to a threshold, the numerator will be the number of subjects with normal baseline with respect to the specific criterion and at least 1 post-baseline outlier value within the analysis period; and denominator will be the number of subjects with normal baseline with respect to the specific criterion and at least 1 post-baseline assessment within the analysis period. When calculating the percentages for the criteria related to change from baseline, the numerator will be the number of subjects meeting the criterion; and denominator will be the number of subjects with a baseline and at least 1 post-baseline assessment within the analysis period. A subject may be counted in multiple categories for a given parameter. All results (regardless of scheduled or unscheduled) will be considered in this summary.

Table 4: Pre-defined Threshold Value for ECG

Parameter	Criteria
PR Interval	>200 msec
QTcF	> 450 msec
QTcF	> 480 msec
QTcF	> 500 msec
QTcF	Increase from baseline >30 msec
QTcF	Increase from baseline >60 msec

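### For the five absolute vital-sign thresholds, SAP 8.8.1 counts only normal-baseline subjects in the numerator but keeps baseline-abnormal subjects in the denominator

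*SAP*

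**What the plan says.** SAP 8.8.1 plans to report "the percentage of patients exceeding pre-defined absolute and relative threshold values across the entire treatment period", and likewise for the safety follow-up period and for both periods together. A single rule covers every criterion in Table 3. The "numerator will be the number of subjects with normal baseline with respect to the specific criterion and at least 1 post-baseline outlier value" in the period, while the "denominator will be the number of subjects with a baseline and at least 1 post-baseline assessment within the analysis period". Three versions are produced: pre-dialysis, post-dialysis and pre-/post-infusion.

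SAP 8.8.3 sets up the same kind of summary for ECG but gives two rules. For threshold criteria the numerator is again limited to normal-baseline subjects, and the "denominator will be the number of subjects with normal baseline with respect to the specific criterion and at least 1 post-baseline assessment". For change-from-baseline criteria "the numerator will be the number of subjects meeting the criterion", over all subjects with a baseline and a later value.

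Protocol 11.4.5.3 and 11.4.5.4 describe the vital-sign and ECG threshold summaries in the same terms. Neither document gives a reason for treating them differently.

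**The concern.** The vital-sign rule pairs the ECG threshold numerator with the ECG change-from-baseline denominator. For an absolute limit, a subject who starts beyond it is removed from the top of the fraction and kept at the bottom. The result is lower than the rate of new abnormality among subjects who could develop one, by an amount that depends on how many were abnormal at the start.

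Two things are at stake. The vital-sign percentages would not mean the same as the ECG percentages reported beside them. And two treatment groups with the same at-risk rate would show different percentages if their baseline abnormality differed. Safety is the primary objective, and vital signs by treatment group and dose belong to a listed secondary safety endpoint (Protocol 3.1.2), so the figure should have a clear meaning.

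**Working it through.** The documents state no figure for this summary, so there is nothing to reproduce. The check is algebra plus illustrations.

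**Which rows are affected (SAP Table 3, 11 rows)**

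- Absolute limits, 5 rows: SBP >180, SBP <95, HR >100, HR <50, respiration rate >24. A baseline value can already breach these. Protocol 4.1 and 4.2 set no entry limit on blood pressure, heart rate or respiration rate, so baseline breaches are possible.
- Change from baseline, 6 rows: two for SBP (such as ">20 mmHg increased or decreased from baseline"), two for weight, two for BMI. At baseline the change is zero, so nobody can meet the criterion then. Read literally, the normal-baseline condition excludes no one.

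**Formula**

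- N = subjects with a baseline and at least one post-baseline assessment in the period.
- q = share of N already abnormal at baseline for the criterion.
- x = normal-baseline subjects with at least one later outlier.
- SAP 8.8.1 percentage = x / N.
- Matched percentage, as in SAP 8.8.3 = x / [N(1 − q)].
- Ratio of the first to the second = 1 − q.

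The 8.8.1 figure can never exceed the matched one. It is strictly lower when q > 0 and x > 0. For the six change rows q = 0, and the two figures are equal.

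**Size, with q assumed because the documents do not give it**

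| q | At-risk rate 10% | At-risk rate 25% | At-risk rate 50% |
|---|---|---|---|
| 0% | 10.0% | 25.0% | 50.0% |
| 5% | 9.5% | 23.8% | 47.5% |
| 10% | 9.0% | 22.5% | 45.0% |
| 20% | 8.0% | 20.0% | 40.0% |

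Each cell is the at-risk rate × (1 − q); for example 25% × 0.8 = 20.0%.

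**Illustration at this trial's group sizes**

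"The randomization ratio within each cohort will be 8:2 (COR-001 to placebo"), and "The placebo subjects at each cohort will be pooled into one group" for the final report. Two cohorts at one dose give 2 × 8 = 16 active subjects. Six cohorts give 6 × 2 = 12 placebo subjects. The abnormal-baseline and outlier counts below are chosen for illustration.

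- Active, N = 16, 2 abnormal at baseline (q = 12.5%), 4 new outliers: 4/16 = 25.0% under 8.8.1; 4/14 = 28.6% matched.
- Placebo, N = 12, none abnormal at baseline, 3 new outliers: 3/12 = 25.0% under both rules.

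The 8.8.1 rule shows two equal groups where the at-risk rates are 28.6% and 25.0%. With the baseline imbalance the other way round, the distortion would reverse.

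**Pre-/post-infusion table**

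Here SAP 8.8.1 takes the baseline from the pre-infusion value at each visit. One subject can therefore be normal before one infusion and abnormal before another. The percentage is per subject over a whole period, and the SAP does not say which status applies.

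**The case against.** The strongest reply is that x / N is a coherent quantity: the share of assessed subjects who developed a new abnormality. It is a biased figure only if the at-risk rate was intended, and SAP 8.8.1 never says that it was. This stands in part. The figure is valid for that description, but the SAP does not give it that label. Nor is it the quantity the SAP announces, since subjects who exceed a limit both before and after baseline are left out of the count. It also conflicts with the ECG rule without explanation.

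The second reply is about scope. A reader might infer that all vital-sign outlier percentages are understated. The documents do not support that: six of the eleven rows are unaffected on a literal reading. Nor does the denominator contain every treated subject; it requires a baseline and a later assessment.

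The third is about size. A reader might infer a large understatement, or a likely distortion between arms that flatters the active drug. Neither document gives any baseline vital-sign data. q is specific to each criterion and may be near zero for some rows. Chance imbalance is possible with 12 placebo subjects, but its size and direction are unknown.

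The last is about consequence. The summary carries no test. Observed values and changes are also tabulated by visit, and clinically significant new abnormalities are to be recorded as adverse events (Protocol 9.1). Those outputs do not correct the percentage, but they make it less likely that a signal would be hidden.

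**Conclusion.** The rule is inconsistent as written, and no other part of the SAP or protocol corrects it. For the five absolute-threshold rows, the percentage equals the at-risk rate times (1 − q). The relative shortfall is q, which the documents do not supply. With q assumed between 0 and 20%, an at-risk rate of 25% is reported as 25% to 20%, and groups with different q cannot be compared directly. For the six change rows there is no numerical effect when the text is read literally. The normal-baseline phrase is undefined there, however, and a programmer who took it to mean a clinically normal value would wrongly exclude subjects from the numerator. The effect is confined to a descriptive safety table; the MTD/DLT rule and the PD endpoints are untouched.

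**What to change.** Amend the percentage rule in SAP 8.8.1 in three places:

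- **Absolute-threshold criteria (five rows).** Restrict the denominator to subjects with a normal baseline for that criterion and at least one post-baseline assessment in the period, as SAP 8.8.3 does for ECG thresholds. Show the denominator for each row, since it will differ by criterion.
- **Change-from-baseline criteria (six rows).** Remove the normal-baseline phrase from the numerator and keep the present denominator. This is a wording clean-up.
- **Pre-/post-infusion table.** State which pre-infusion value fixes a subject's baseline status across the analysis period. The ECG wording does not settle this, so it needs its own sentence.

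The cost is a few sentences in the SAP and matching changes to the table shells and programs. No new data are needed, and the first two changes reuse rules already in the SAP.

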8.8.2 Physical Examination

A subject listing of physical exam findings of signs of infection will be provided.

In addition, Physical examination clinically significant new or worsening findings will be reported as adverse events and will therefore be summarized as described for adverse events.

8.8.3 12-Lead ECG

ECG interpretation (normal vs. abnormal) will be summarized using frequency and percentage at each visit by treatment group. Observed values and change from baseline in ECG intervals (PR, QT, HR, and QTcF), rhythm and heart rate will be summarized descriptively at each visit by treatment group.

The percentage of patients exceeding pre-defined absolute and relative threshold values across the entire treatment period, across the entire safety follow up period, and across both of these periods will be summarized (see [Table 4](#)). When calculating the percentages for the criterion related to a threshold, the numerator will be the number of subjects with normal baseline with respect to the specific criterion and at least 1 post-baseline outlier value within the analysis period; and denominator will be the number of subjects with normal baseline with respect to the specific criterion and at least 1 post-baseline assessment within the analysis period. When calculating the percentages for the criteria related to change from baseline, the numerator will be the number of subjects meeting the criterion; and denominator will be the number of subjects with a baseline and at least 1 post-baseline assessment within the analysis period. A subject may be counted in multiple categories for a given parameter. All results (regardless of scheduled or unscheduled) will be considered in this summary.

Table 4: Pre-defined Threshold Value for ECG

Parameter	Criteria
PR Interval	>200 msec
QTcF	> 450 msec
QTcF	> 480 msec
QTcF	> 500 msec
QTcF	Increase from baseline >30 msec
QTcF	Increase from baseline >60 msec

8.9 ANTIBODIES TO COR-001

The immunogenic potential of COR-001 will be assessed by summarizing the number and percentage of patients who develop detectable anti-drug antibodies (ADA) by dose. Anti-drug antibody titers will be summarized descriptively for ADA positive samples and the impact of ADA on PK will be assessed if data allows. Neutralizing capacity of any detected ADA will be summarized.

9. PHARMACOKINETIC ANALYSIS AND PHARMACOKINETIC/PHARMACODYNAMIC ANALYSIS

A patient listing of all serum concentration-time data for each dose group will be presented. High-sensitivity CRP (hsCRP) and serum IL-6 will also be presented in listings. Analyses of PK and PK-PD modeling are described in the Data Analysis Plan for Pharmacokinetics and Pharmacokinetic-Pharmacodynamic Modeling.

10. INTERIM ANALYSES AND SAFETY REVIEW COMMITTEE (SRC)

10.1 SAFETY REVIEW COMMITTEE

A Safety Review Committee (SRC) is established and will apply its judgment to the conduct of this study in order to ensure the safety of study participants. The SRC will review unblinded safety data prior to dose escalation (i.e., higher total dose than studied in the preceding cohorts). The reviews will occur after all patients in a cohort have completed 21 days of treatment (or last visit, if prematurely discontinued). The Sponsor will consider SRC recommendations when determining the dose for the next cohort. Following completion of the dose-escalation phase of the study, the SRC will meet approximately every 1 - 2 months until all subjects have completed safety follow-up period or terminated early to review accruing safety data.

The full activities and responsibilities of the SRC are described in the SRC charter.

10.2 INTERIM ANALYSIS

A single interim analysis will be conducted for the purpose of guiding future COR-001 clinical program activities. There are no stopping rules associated with the interim analysis and therefore no statistical adjustment for multiplicity will be made. The interim analysis will be conducted, at earliest, once all cohorts below that which exceed the MTD, excluding any expansion cohorts, have completed the study through Week 4 (or final visit, if prematurely discontinued).

The following endpoints will be assessed in the interim analysis:

- PD parameters: hsCRP, SAA, free and/or total serum IL-6, as well as, hemoglobin, TSAT, CHr, pre-albumin, and albumin
- Change in hemoglobin from screening to peak hemoglobin (defined as per subject absolute maximal hemoglobin in g/dL)
- Change from baseline (mean of Full Screening and Day 1 values) in Hemoglobin to Weeks 10-12, excluding hemoglobin values following a change in the total weekly ESA dose. A change is defined as the first time when the ESA weekly dose goes up by >25% or down by >25% relative to the previous week's dose.
- ERI
- Hemoglobin and ERI stratified by baseline ERI (<median or >=median)
- Cardiac biomarkers: Pro-NT-BNP and troponin
- MRI outcome: LVMI, LVESVI, LVEDVI, and LVEF
- Handgrip strength
- FACIT fatigue score

The summary approach for these listed endpoints will be the same as described in the SAP and will follow the specifications below for presentation in order to mask the treatment-level data:

- By masked treatment group (e.g. Treatment A, Treatment B, and etc.). Subjects receiving placebo from all cohorts will be combined as one of the treatment groups
 - Both PD analysis population and Per-Protocol analysis population will be performed on masked data
- Pooled treatment vs pooled placebo
- Pooled responder analysis defined as change from baseline in PD parameter for all patients (regardless of active vs placebo assignment) who achieve a $\geq 50\%$ reduction in hsCRP

To avoid identification of individual patients, the number of subjects, minimum, maximum values, and raw numbers for the percentages (i.e. numerator and denominator) will not be presented. Only the means, standard deviations, and percentages will be presented. The sponsor personnel will only receive the masked treatment group-level information and have no access to actual treatment-level information nor subject-level treatment information.

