3.3.2 Blinding

This study is double-blind. The patients, investigators, site personnel (not including site personnel responsible for drug versus placebo preparation), site monitors and Sponsor clinical operational personnel will be blinded to the treatment assignment. The Sponsor representative(s) on the SRC will become unblinded for the safety reviews of each cohort in order to select doses for the next cohort. The SRC will be unblinded. In addition, contract research organization (CRO) personnel analyzing the PK samples and performing the PK, target engagement, and analysis of PK/pharmacodynamic relationships and those responsible for interactive web-response system (IWRS) will have access to the randomization list. The randomization list will be generated by a CRO statistician not otherwise involved in the study or the SRC unblinded statistician.

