2.2 DEFINITIONS OF ANALYSIS SETS

The number of subjects entered, the number and the percentage of subjects included in each analysis set, and the number and the percentage of subjects excluded from each analysis set will be presented by dose group, treatment and overall.

Intent-to-treat (ITT) analysis population: The ITT analysis population will be defined as all randomized patients. Treatment classification will be based on the randomized treatment. This will be the primary population for the analyses of disposition and baseline data.

Pharmacodynamic analysis population: The pharmacodynamic population will be defined as all ITT patients who were treated with their assigned study drug treatment, had any pharmacodynamic assessments, and did not have certain important protocol deviations described below. This will be the population for the pharmacodynamic analyses.

- ≥ 2 Missed doses or ≥ 2 incorrect doses
- Important protocol deviations that are determined to significantly affect interpretation of PD endpoints, identified prior to unblinding of the study.
 - Minor departures from the ESA dosing guidelines in the protocol will not be considered major deviations.

For subjects who do not receive the assigned dose at any time during treatment, the dose will be defined as the highest dose received.

Pharmacokinetics analysis population: The PK population will be defined as all patients who have any valid samples measured for Study Drug levels. This will be used for PK analysis.

Safety analysis population: The safety analysis population will consist of all patients randomized and treated with any amount of study medication (COR-001 or placebo). Treatment classification will be based on the actual treatment received. This population will be used for the safety analyses.

MTD analysis Population: The MTD analysis population will be a subset of safety analysis population by excluding subjects replaced due to a non-safety reason. This population will be used for MTD and DLT analyses.

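### The SAP's interim displays undo the treatment-level masking that SAP 10.2 promises: the pooled table discloses the placebo result and shows which coded group is placebo

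*SAP*

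**What the plan says.** SAP 10.2 introduces its display rules as being "in order to mask the treatment-level data". The first display is by coded group (Treatment A, Treatment B and so on), where "Subjects receiving placebo from all cohorts will be combined as one of the treatment groups". The second is "Pooled treatment vs pooled placebo". The third is a responder summary that ignores treatment assignment. Group sizes, minima, maxima and raw counts are suppressed: "Only the means, standard deviations, and percentages will be presented". The section ends: "The sponsor personnel will only receive the masked treatment group-level information and have no access to actual treatment-level information nor subject-level treatment information".

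Protocol 11.5 is looser. It lets sponsor personnel have information by treatment group and bars only subject-level information. Protocol 3.3.2 keeps the sponsor's clinical operations staff blinded.

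Both documents allow the interim once the non-expansion cohorts below the one that exceeded the MTD have reached Week 4. Protocol 4.5 leaves replacement of patients who drop out for non-safety reasons to the sponsor. SAP 2.2 removes patients from the PD population for "Important protocol deviations that are determined to significantly affect interpretation of PD endpoints, identified prior to unblinding of the study".

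**The concern.** The masking depends on a reader being unable to tell which coded column is placebo. If the same reader also holds a table with a placebo column made up of the same patients, matching the two takes no statistical skill. The final sentence of SAP 10.2 would then describe a safeguard that the tables do not provide.

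Two kinds of sponsor decision could be affected. Whether to replace a drop-out is discretionary. Whether a deviation is important enough to exclude a patient from the PD population is a judgement that the SAP protects by requiring it before unblinding. That protection is weaker if the people deciding already know the placebo and active results on the PD endpoints.

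**Working it through.** The documents give no figure to reproduce here. The check is mainly one of logic, with a simulation to see whether rounding could hide the match.

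**Step 1: same patients in both tables.** SAP 7 pools all placebo patients for the PD endpoints. SAP 10.2 puts all placebo patients into one coded group. If both displays use the PD population, the pooled-placebo column and one coded column contain the same patients, so mean and SD agree exactly for every endpoint.

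**Step 2: would coding the pooled columns help?** SAP 1.2.3 names three active regimens (2, 6 and 20 mg). Pooled active is therefore a mixture and will not in general equal any one coded group. The column that repeats is placebo.

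**Step 3: does rounding hide it?** Assumed group sizes are Cohorts 1-5 at the actual doses in Protocol 3.5.4, filled at 8:2:
- 2 mg: 2 × 8 = 16
- 6 mg: 2 × 8 = 16
- 20 mg: 1 × 8 = 8
- placebo: 5 × 2 = 10

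The SD was 17.3 and the active-placebo difference 0 or -10.6 (the hsCRP planning values in SAP 1.3.2). There were 4,000 runs with nine endpoints, simulated as independent and all on this scale.

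| Rounding | Unique placebo match, one endpoint | Unique match, nine endpoints | Pooled active matches a coded column by chance |
|---|---|---|---|
| Whole numbers | 98.8% (difference 0), 99.4% (-10.6) | 100% | 4.8%, 4.1% |
| 1 decimal | 100% | 100% | 0.05%, 0.025% |
| 2 decimals | 100% | 100% | 0% |

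**Step 4: timing.** Doses fall on Days 1, 15, 29, 43, 57 and 71; the Week 12 visit is Day 78 (Protocol Appendix A).
- Week 4 visit on Day 22: 2 doses given, 6 - 2 = 4 remaining, 78 - 22 = 56 days to the Week 12 visit.
- Day 29, which SAP 7.1 uses as the Week 4 value for hsCRP: 3 doses given, 6 - 3 = 3 remaining, 78 - 29 = 49 days.

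Expansion cohorts do not count toward the trigger and may be at any stage.

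**Step 5: access rules side by side.** SAP 10.2 allows masked group-level data only. Protocol 11.5 allows group-level data without requiring masking. Both bar subject-level data. The displays in SAP 10.2 fit the protocol's rule but not the SAP's own.

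**The case against.** The strongest reply is that Protocol 11.5 permits group-level knowledge, the interim has no stopping rules and serves programme planning, and no patient is identified. That is correct. It makes this a failure of the SAP's own promise and a mismatch between documents, not a breach of the protocol. The pooled table might also be meant for other readers, but the SAP names none and lists it under the same rules. Week 4 is only the earliest date: the listed Weeks 10-12 hemoglobin and MRI endpoints suggest a later interim, so patients still on treatment are a possibility. Nor do the documents say that the interim's readers are the people who decide replacements or deviations.

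A reader might infer more than the documents support:
- **That any one endpoint identifies placebo with certainty.** With whole-number rounding, a single endpoint left 0.6-1.2% of simulated runs ambiguous, and the match needs the same population in both tables.
- **That percentages reveal the group**, because 30% or 40% can arise only with 10 placebo patients. One exclusion from a 16-patient arm gives 6/15 = 40%. A sixth cohort makes placebo 12, where neither value is attainable.
- **That individual arms are exposed.** Guessing an arm from a patient's hsCRP is a further step that the duplicated column does not supply.
- **That DLT queries are compromised.** The DLT window is Days 1-21, already closed for cohorts that have reached Week 4.
- **That SAP 10.2 contradicts Protocol 3.3.2**, where "The Sponsor representative(s) on the SRC will become unblinded for the safety reviews of each cohort". That concerns safety reviews. The statement that sponsor personnel "have no access to actual treatment-level information nor subject-level treatment information" can be read as covering the interim package only.
- **That the active doses are decoded too.** The expected hsCRP pattern in Protocol 3.5.4 makes an ordering plausible, but the documents do not establish it.

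**Conclusion.** The point holds in limited form, and SAP 10.2 should be changed. As written, it does not deliver the masking that it states. The pooled table gives the placebo result directly, and its match with one coded column labels that group as placebo and the rest as active. This rests on three assumptions: both displays reach the same sponsor readers, both use the same population, and more than one active dose is included. The SAP attaches the PD and per-protocol populations explicitly only to the coded display; that the pooled table uses the PD population follows from SAP 7. The match does not depend on the assumed group sizes. Any bias would come through replacement and PD-population decisions made after release. Its size cannot be estimated from the documents.

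**What to change.** Choose one of two routes in SAP 10.2.

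1. **Keep the masking.** Send blinded sponsor staff only the coded by-group tables. Send the pooled active-versus-placebo table only to a named, firewalled group that takes no part in replacement or PD-population decisions. Sending blinded staff the pooled table alone would not do, because it still discloses the placebo result. Coded tables alone may still allow a guess from the hsCRP pattern, but no longer an exact match.
2. **Declare it.** State that the interim is unblinded at group level, list the recipients, and require deviation and PD-population decisions for the data in hand to be fixed before release.

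In either case, make the access sentences in SAP 10.2 and Protocol 11.5 agree.

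The cost is wording and a distribution list. Under the first route fewer sponsor staff see the pooled contrast; under the second, the deviation review must be done earlier. Design, sample size and dosing are unaffected.
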